## **2.0 STUDY OBJECTIVES**

The objectives of this study are to evaluate outcomes of the Lapiplasty® Procedure using the Lapiplasty® Mini-Incision™ System for patients in need of hallux valgus surgery:

1. To determine radiographic recurrence of hallux valgus and the timing of failure following hallux valgus correction with the Lapiplasty® Procedure.
2. To determine whether the Lapiplasty® Procedure effectively corrects anatomical alignment of the 1st metatarsal and sesamoids in all three planes.
3. To assess whether early weight-bearing after the Lapiplasty® Procedure affects the union rates or causes loss of 3-plane correction.
4. To evaluate the quality of life and pain scores following the Lapiplasty® Procedure.

## **3.0 STUDY ENDPOINTS**

### **Primary:**

Radiographic recurrence of hallux valgus deformity at 24 months for subjects with successful correction (defined as IMA <9.0°, HVA <15.0° and TSP as ≤ 3 at 6 weeks post-Lapiplasty® Procedure). Recurrence is defined by any two of the following three criteria being met at 24 months post-procedure: IMA of ≥12°, HVA ≥20° and TSP ≥4.

### **Secondary:**

1. Change in radiographic angular/positional alignment before and after the Lapiplasty® Procedure [Time Frame: pre-operatively, 6 weeks, 4 months, 6 months, 12 months, and 24 months, post-Lapiplasty® Procedure].
2. Evaluate clinical/radiographic healing (union vs non-union). Non-union defined as lucency at TMT joint, hardware failure and/or loss of correction (recurrence), plus clinical pain at first TMT joint at 12 months post- Lapiplasty® Procedure.
3. Clinical complications through 24-month follow-up visit due to the Lapiplasty® System Implants, the Lapiplasty® Procedure, the post-operative weight-bearing protocol or health conditions that could affect other outcome measures.
4. Time to start weight-bearing in a boot, in days.
5. Time to start weight-bearing in shoes, in days.

6. Time to return to full unrestricted activity, in days.
7. Change in pain at the base of the big toe (bunion related) assessed via a Visual Analog Scale (VAS) at 0-14 days, 14-21 days, 6 weeks, 4 months, 6 months, 12 months and 24 months post-Lapiplasty® Procedure, in comparison to baseline visit pain.
8. Change in Quality of Life, (PROMIS-29, PROMIS-25 and MOxFQ) defined as the total score measured at 6 months, 12 months and 24 months post-Lapiplasty® Procedure, in comparison to baseline visit.
9. Change in Range of Motion - 1st MTP dorsiflexion and plantarflexion at 12 months and 24 months post-Lapiplasty® Procedure, in comparison to baseline visit.
10. Change, if any, in initial incision length during Lapiplasty® Procedure.
11. Change in radiographic foot length and width at 12 months post-Lapiplasty® Procedure in comparison to baseline visit.
12. Change in swelling at 6 weeks and 4 months post-Lapiplasty® Procedure as compared to 0-2 week visit.
13. Change in scar quality at 4 months, 6 months, and 12 months post-Lapiplasty® Procedure in comparison to baseline visit.
14. Correlation between amount of time external positioner is actively used during Lapiplasty Procedure with necrosis, blistering, bruising and tissue ulceration events.

[figure not shown]
### **Secondary Endpoints – Health Economic Outcomes**

All health economic endpoints are exploratory in nature.

1. Complications below that are related to the Lapiplasty® Procedure or the Lapiplasty® System Implants requiring subsequent secondary surgical interventions, defined as the following: 1) deviations/delay from normal operative plan 2) readmission to hospital 3) return to operating room 4) unscheduled visits due to complications 5) employment of home health services;
  - a. Revisions
  - b. Hardware removals
  - c. Reoperations
  - d. Supplemental fixations
  - e. Wound healing requiring surgical intervention
  - f. Infection at surgical site requiring surgical intervention
2. Time to return to work (or normal household activities if non-working), in days, while noting work status and work classification (sedentary, light work, medium work, heavy work, very heavy work).
3. Time to return to full work, in days (or full household activities if non-working), while noting work status and work classification (sedentary, light work, medium work, heavy work, very heavy work).
4. Post-operative physical therapy requirements required for recovery of the Lapiplasty® Procedure.

#### 4.0 INVESTIGATIONAL PLAN

##### 4.1 Overall Study and Design – Subject Disposition Diagram

## Overall Study and Design – Description

Patients 14 years through 58 years with symptomatic hallux valgus will be eligible to participate based on the inclusion and exclusion criteria defined in this protocol.

The overall plan for all subjects consists of the following elements:

- Patients will be informed about the nature of the research, given the ICF to read, and if the patient understands and agrees to the procedure, they will be asked to provide written informed consent. Subjects are considered **enrolled** in the study when they have signed an informed consent;
- Subjects will undergo screening procedures during the baseline visit to determine if inclusion and exclusion criteria are satisfied and the subject is eligible for the study procedure;
- Subjects must meet all inclusion/exclusion criteria before being **treated** in the study. If any eligibility criteria (including intra-operative criteria) are not satisfied, the subject will be considered a screen failure and will not be considered treated in the study;
- Subjects will undergo the Lapiplasty® Procedure, per protocol. Subjects are considered **treated** in the study when biplanar plating at the TMT joint is complete **and** the incision length is confirmed to meet criteria;
- Subjects will be followed for up to 2 years post index procedure to evaluate outcomes and potential complications;
- Subjects will be assessed for AEs and will be instructed to notify the PI of any AEs that occur during the entire course of the study. Data will be recorded into subject source medical records.

## 4.2 Selection of Study Population

### 4.2.1 Recruitment

All patients who meet the inclusion criteria will be tracked on a Screening Log. Patients who meet inclusion criteria will be provided with the IRB approved ICF and will have the opportunity to read, understand, and have their questions answered prior to signing the ICF. If the patient agrees to participate in the study and signs consent, the ICF will be completed. The subject must sign and date the ICF prior to any study-specific procedures being performed. The person reviewing the ICF with the subject will also sign and date the ICF. The subject will be given a copy of the signed ICF to keep.

All subjects who sign the ICF will be documented on a paper Screening and Enrollment Log. All subjects who sign the ICF will be entered in the EDC.

Upon entering subject enrollment information into the EDC, each subject will be assigned a unique ID number sequentially in ascending order.

### 4.2.2 Enrollment and Treatment

- Subjects are considered **enrolled** in the study once the informed consent has been signed by the patient. Subjects who sign a consent document, but do not meet inclusion/exclusion criteria (including intra-operative criteria) will be considered a screen failure. Subjects are considered **treated** in the study when the biplanar plating is complete **and** the incision length is confirmed to meet criteria.

#### 4.2.3 Inclusion Criteria

Patients satisfying the following criteria will be considered the screening population and will be eligible for participation:

1. Male and females between the ages 14 and 58 years at the time of consent;
2. Closed physal plates at the time of consent;
3. Intermetatarsal angle is between 10.0° - 22.0°;
4. Hallux valgus angle is between 16.0° - 40.0°;
5. Willing and able to adhere to early weight-bearing instructions post-operatively;
6. Capable of completing self-administered questionnaires;
7. Acceptable surgical candidate, including use of general anesthesia;
8. Female patients must be of non-childbearing potential or have a negative pregnancy test within 7 days prior to index procedure;
9. Willing and able to schedule index procedure within 3 months of consent and able to return for scheduled follow-up visits;
10. Willing and able to provide written informed consent.

#### 4.2.4 Exclusion Criteria

Patients satisfying the following criteria will not be eligible for participation:

1. Previous surgery for hallux valgus on operative side;
2. Previous surgeries on operative foot involving fusion of foot or ankle joints (other than hammertoe or lesser toes/digits);
3. Additional concomitant procedures outside of the 1st ray;
4. Moderate or Severe osteoarthritis of the MTP joint based on radiographic imaging (including lack of evident crista) or positive grind test;
5. Symptomatic flatfoot or asymptomatic flatfoot (defined as calcaneal inclination <5° and talonavicular subluxation/uncovering >50%);
6. BMI >40 kg/m^2;
7. Current nicotine user, including current use of nicotine patch;
8. Current clinical diagnosis of diabetes with fasting plasma glucose > 126 mg/dL and/or HbA1c ≥7.0;
9. Current clinical diagnosis of peripheral neuropathy or by assessment on 4-point monofilament test;
10. Current clinical diagnosis of fibromyalgia;
11. Current clinical diagnosis of Complex Regional Pain Syndrome/Reflex Sympathetic Dystrophy (CRPS/RSD);
12. Current uncontrolled hypothyroidism;
13. Previously sensitized to titanium;
14. Currently taking oral steroids or rheumatoid biologics;

15. Currently taking immunosuppressant drugs;
16. Insufficient quantity or quality of bone to permit stabilization, conditions that retard healing (not including pathological fractures) and conditions causing poor blood supply such as peripheral vascular disease;
17. Active, suspected or latent infection in the affected area;
18. Use of synthetic or allogenic bone graft substitutes;
19. Current diagnosis of metatarsus adductus (defined as  $MAA \geq 23^\circ$ );
20. Known keloid and hypertrophic scar forming;
21. Scheduled to undergo a same-day bilateral procedure. Patient agrees to refrain from the Lapiplasty® Procedure (or other hallux valgus procedures) on contralateral foot for minimum of 6 months post index procedure;
22. Patient has previously been enrolled into this study for a contralateral procedure;
23. Scheduled for any concomitant procedure that would alter patient's ability to early weight-bear post-procedure;
24. Patient requires an incision  $>4.0$  cm to complete the procedure (determined pre-operatively or intra-operatively);
25. Patient is actively involved with a workman's compensation case or is currently involved in litigation;
26. Patient is currently or has participated in a clinical study in the last 30 days prior to signing informed consent or is considering participation in another research protocol during this study. Exceptions to this include survey clinical studies with no treatment or if subject is greater than 12 months post procedure in the Treace ALIGN3D™ study without ongoing protocol defined AE; these are not exclusionary;
27. Patient has a condition or finding that, in the opinion of the Investigator, may jeopardize the patient's well-being, the soundness of this clinical study, or could interfere with provision of informed consent, completion of tests, therapy, or follow-up.

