## Schedule of Assessments

Study Activity	Visit 1	Visit 2	Visit 3	Visit 4	Visit 5	Visit 6	Visit 7	Visit 8	Visit 9	Study Exit
	Baseline 	Index Procedure	0-14 Day follow-up	14-21 Day follow-up (+3 days)	6 Week follow-up (±2 weeks)	4 Month follow-up (±2 weeks)	6 Month follow-up (±1 month)	12 Month follow-up (±1 month)	24 Month follow-up (±2 months)	
Informed Consent	X									
Demographics	X									
Medical and Surgical History	X	X								
Targeted Physical Exam	X									
Height / Weight 	X									
Blood Collection, if required 	X									
4-Point Monofilament Test, if required 	X									
Radiographic Imaging 	X				X	X	X	X	X	
VAS Pain Scale	X		X	X	X	X	X	X	X	
POSAS						X	X	X	X	
QOL Measurements 	X						X	X	X	
Medications Review	X	X	X	X	X	X	X	X	X	
Digital Photos of Foot	X	X	X	X	X	X	X	X	X	
Clinical Exam of Foot	X		X	X	X	X	X	X	X	
Foot Measurements	X	X	X	X	X	X	X	X		
Pregnancy Test (if applicable) 	X									
Inclusion/Exclusion Criteria	X 	X 								
Index Procedure		X								
Wound check/surgical site healing			X	X	X	X				
Return to Weight-Bearing Activities 			X	X	X	X	X			
Range of Motion 	X					X	X	X	X	
Secondary Surgical Interventions 			X	X	X	X	X	X	X	
Adverse Events Assessment 		X	X	X	X	X	X	X	X	
Radiographic Measurements 	X				X	X	X	X	X	
Health Economic Outcomes 			X	X	X	X	X	X	X	
General Satisfaction Questionnaire									X	
Study Exit										X

 Baseline visit study activities must occur within 90 days of the Index Procedure unless otherwise noted.

 BMI should be calculated from height and weight measurement to determine patient eligibility.

 Blood collection is required only if subject has diagnosis of diabetes to determine fasting plasma glucose levels or HbA1c.

 4-point monofilament test is required only if subject has diagnosis of diabetes or if warranted by PI to assess for peripheral neuropathy.

 Three radiographic views of the operative foot should be obtained per visit (weight-bearing AP, lateral and axial views of operative foot). The axial view should be collected using the study provided axial positioner.

 QOL assessment tools – MOxFQ and PROMIS-29 (PROMIS-25 for ages 14-17).

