**Index Procedure** – See **Section 7.2** for complete list of data collected during the Index Procedure. Concomitant procedures of the 1st ray should also be recorded. These include but are not limited to, akin osteotomy, bone graft harvest (synthetic or allogenic bone graft substitutes are not permitted), intercuneiform stabilization, traditional medial eminence resection, rongeur of the medial capsular ridge, and/or dorsal metatarsal bone resection. No concomitant procedures that alter the post-operative WB instructions are permitted (including evans and other calcaneal osteotomies, lesser TMT joint fusions, lisfranc or metatarsus adductus). Any complications during the procedure or deviations to the normal operative plans must also be recorded.

**POSAS:** See **Appendix 9**. The Patient and Observer Scar Assessment Scale will be collected per the Assessment instructions.

**Return to Weight-Bearing Activities** – The actual date that the subject was allowed to start to return to weight-bearing activities (protected WB in CAM boot, shoe and full unrestricted activities) should be recorded. The number of days from index procedure will be calculated by Clinindex. See **Section 5.3** for post-operative care and weight-bearing instructions.

**Secondary Surgical Interventions:** Any adverse event/complication that requires a subsequent secondary surgical intervention should be recorded. The reason for the subsequent surgical intervention and the action taken should be recorded. Subsequent secondary surgical interventions are defined as revisions, hardware removals, reoperations, supplemental fixations or other surgical intervention due to wound healing issues or infections at surgical site.

**Health Economic Outcomes:** The date the subject was allowed to return to work (or normal household activities if non-working), should be recorded while noting work status and work classification (sedentary, light work, medium work, heavy work, very heavy work). The date the subjects was allowed to return to full work (or full household activities if non-working), should be recorded while noting work status and work classification (sedentary, light work, medium work, heavy work, very heavy work – See **Appendix 1** for definitions). Any post-operative physical therapy requirements required for recovery of Lapiplasty® Procedure should be recorded. Any employment of home health services and the reason should be recorded.

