### **9.3 Analysis Population**

Intent-to-Treat (ITT) population: The ITT population is defined as all enrolled subjects who were treated with the Lapiplasty® Procedure using the Mini-Incision™ System.

Per-Protocol (PP) Population: The per-protocol population is defined as all enrolled subjects who were treated with the Lapiplasty® Procedure using the Mini-Incision™ System who did not experience a major protocol violation. Major protocol violations include, but are not limited to, subjects who:

- Entered the study although they did not satisfy the eligibility criteria;
- Completed incorrect version of PROMIS based on age of subject;
- Did not return to protective weight-bearing activities by 3 weeks (+3 days);
- Received Lapiplasty® Procedure (or other hallux valgus procedures) on contralateral foot less than 6 months after initial index procedure; or
- Developed withdrawal criteria during the study but were not removed from study participation.

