6.4 Derived Variables

6.4.1 “Time To” variables

“Time to” variables such as time to follow-up, time to weight-bearing, and time to return to work will be computed in days as (date of interest - date of index procedure). “Time to” will be computed in weeks as (date of interest - date of index procedure)/7. “Time to” will be computed in months as (date of interest - date of index procedure)/30. “Time to” will be computed in years as (date of interest - date of index procedure)/365.25.

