7.2.2 Secondary Effectiveness Analysis

Effectiveness analyses will be performed on the following secondary endpoints:

- 1) Percentage of subjects with recurrence at 12 months where recurrence is defined as meeting 2 of the following 3 criteria: IMA of $\geq 12^\circ$, HVA $\geq 20^\circ$ and TSP ≥ 4 .

- 2) Percentage of subjects with recurrence at 12 months and 24 months where recurrence is defined as HVA >15°.
- 3) Percentage of subjects with recurrence at 12 months and 24 months where recurrence is defined as HVA >20°.
- 4) Percentage of subjects with successful correction at 6 weeks.
- 5) Change from baseline in radiographic angular/positional alignment for HVA, IMA, TSP, and sagittal plane at 6 weeks, 4 months, 6 months, 12 months, and 24 months.
- 6) Percentage of subjects with non-union (absence of clinical/radiographic healing) at 12 months.
- 7) Time to weight-bearing in a controlled ankle motion (CAM) boot, in days.
- 8) Time to weight-bearing in shoes, in weeks.
- 9) Time to return to full unrestricted activity, in months.
- 10) Change from baseline in pain at the base of the big toe (bunion related) assessed via VAS at 0-14 days, 14-21 days, 6 weeks, 4 months, 6 months, 12 months, and 24 months.
- 11) Change from baseline in Quality of Life at 6 months, 12 months, and 24 months as measured by PROMIS-29 (for adult subjects), PROMIS-25 (for pediatric subjects), and MOxFQ (for all subjects).
- 12) Change from baseline in range of motion of the 1st MTP dorsiflexion, plantarflexion, and dorsiflexion plus plantarflexion at 4 months, 6 months, 12 months, and 24 months.
- 13) Change from baseline in foot swelling measurements at 0-14 days, 14-21 days, 6 weeks, 4 months, 6 months, and 12 months.
- 14) Summary of POSAS responses over time at 4 months, 6 months, 12 months, and 24 months.

Statistical summaries will be produced in accordance with section 7, and listings will be generated by site, subject, and visit (where applicable) within subject.

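### Contralateral bunion surgery is permitted from month 6 but no listed field records it, so PROMIS change at 12 and 24 months (and at a late Visit 7) can include recovery of the other foot

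*Protocol*

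**What the plan says.** **When the other foot may be operated on.** Exclusion 21 in Protocol 4.2.4 rules out same-day bilateral surgery and has the subject refrain from hallux valgus procedures "on contralateral foot for minimum of 6 months post index procedure". The analysis sets carry the same boundary. Protocol 9.3 lists as a major violation a subject who "Received Lapiplasty® Procedure (or other hallux valgus procedures) on contralateral foot less than 6 months after initial index procedure", and Protocol 8.2.2 and SAP 6.2.2 repeat it. Neither document has a rule for surgery at or after six months.

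**When outcomes are measured.** The Schedule of Assessments gives the windows as "6 Month follow-up (±1 month"), "12 Month follow-up (±1 month") and "24 Month follow-up (±2 months"). PROMIS and MOxFQ are completed at all three visits. SAP 7.2.2 item 11 analyses "Change from baseline in Quality of Life at 6 months, 12 months, and 24 months as measured by PROMIS-29" for adults, with PROMIS-25 for minors and MOxFQ for everyone.

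**What is recorded about surgery after the index procedure.**
- Medical and surgical history is scheduled at Visits 1 and 2 only.
- Planned surgery is noted at baseline (Protocol 7.1 and 7.12).
- Under secondary surgical interventions, Protocol 7.12 says: "Any adverse event/complication that requires a subsequent secondary surgical intervention should be recorded".
- Adverse events reach the eCRF only if related to the index procedure or implants (schedule footnote 14). Foot surgery already planned at consent is exempt from adverse event reporting (Protocol 10.2.4).
- The visit lists in Protocol 7.7 to 7.9 contain no item on contralateral surgery.

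**The concern.** The sponsor already treats contralateral surgery before six months as serious enough to remove a subject from the per-protocol set. From month 6 the same event is compliant, and the plan gives no way to see it.

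This matters most for PROMIS. Its items on stairs, a 15-minute walk, chores, social roles, pain interference and average pain are not tied to a foot. A subject recovering from the second operation will report that recovery, and the value enters the change from baseline after the index procedure.

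MOxFQ asks about the foot under treatment and offers left, right or both. After a second operation a subject may reasonably answer for the other foot or for both, and SAP 6.4.4 does not say which side is scored.

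Objective 4 concerns quality of life and pain. SAP section 7 applies two-sided t-tests to change from baseline, and SAP 6.3 uses available data without a rule for this event. If the date is not collected as subjects are seen, the plan cannot show how many values are affected or whether it matters.

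**Working it through.** The plan states no figure to reproduce: Protocol 9.2 says the 200 subjects do not come from a formal calculation. The check is therefore of the calendar, followed by an illustration of size.

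**Inputs from the documents**
- Earliest permitted contralateral surgery: month 6 (Protocol 4.2.4).
- Visit windows: 6 ± 1, 12 ± 1 and 24 ± 2 months (Schedule of Assessments).
- Days per month: 30. SAP 6.4.1 defines this for time-to variables ("will be computed in months as (date of interest - date of index procedure)/30"), and I borrow it for the windows. Month 6 is then day 180.
- Recovery yardstick: 4 months, or 120 days, the point at which Protocol 5.3 has low-impact exercise begin after the index procedure. Applying it to the other foot is an assumption.

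**Calendar.** Suppose, for illustration, that second operations are spread evenly over days 180–720, which is 540 days.

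| Visit | Window (days) | Visit day taken | Permitted surgery days in the preceding 120 | Share of operations |
|---|---|---|---|---|
| 7 | 150–210 | 180 | 0 | 0% |
| 7 | 150–210 | 210 | 30 | 30/540 = 5.6% |
| 8 | 330–390 | 360 | 120 | 120/540 = 22.2% |
| 9 | 660–780 | 720 | 120 | 120/540 = 22.2% |

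The six-month limit falls at the midpoint of the Visit 7 window. A compliant subject can be at most 210 − 180 = 30 days past a second operation at that visit, and only if it is held after day 180. At day 210 both the 7-day PROMIS recall and the 4-week MOxFQ recall could lie wholly after the operation. Visits 8 and 9 are the more exposed.

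**Size.** Shift in mean change = share of subjects measured during recovery × T-score loss. Neither factor is in the documents.
- Low: 0.05 × 5 = 0.25 points (10 of 200 subjects).
- High: 0.10 × 10 = 1.0 point (20 of 200 subjects).
- Wider range: 0.05 × 3 = 0.15 to 0.30 × 10 = 3.0 points.

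Under the even spread, 5% in recovery at one visit needs 0.05/0.222 = 22.5% of subjects to have the second operation during days 180–720, and 10% needs 45%. The 30% case would need 135%, which is impossible, so 3.0 points could arise only if operations clustered before a visit.

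**Yardstick for size.** The 95% half-width of a mean change at n = 200 is 1.96 × SD/√200: 1.11 points for SD 8 and 1.39 for SD 10. The SD of change is not given; 10 is the PROMIS reference SD in SAP 6.4.5. The SAP tabulates adults and minors separately (Tables 22 and 23) and 200 is the maximum enrollment, so actual half-widths would be larger.

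**The case against.** The strongest reply is that most of the trial is shielded.
- The VAS is restricted to the operative foot (Protocol 7.12).
- Range of motion and radiographs are taken on the operative foot, and the primary endpoint is radiographic.
- MOxFQ is asked by treated side.
- The study is single-arm and mainly descriptive (Protocol 9.0), and quality of life is one of 14 secondary endpoints.
- The illustrative shift of 0.25–1.0 points is smaller than the sampling half-width.

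All of this stands, and it confines the point to PROMIS first and MOxFQ second. It does not remove it, because this bias does not shrink with more subjects and the plan has no count by which to show that it is small.

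A second reply is that contralateral surgery may be traceable. Sites must identify it before six months to apply the deviation rule, plans are noted at baseline, medications for foot pain go on the eCRF, and source documents include clinic records. This also stands in part. A reader might infer that no later analysis could ever separate the affected values, but the eCRF itself is not in the documents and these traces exist. What can be said is that no listed field gives the occurrence and date.

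A reader might also infer that return-to-work dates are equally exposed. What is recorded is the date the subject was allowed to return, so only subjects not yet cleared by month 6 could be touched. Nor do the documents contain any figure showing that an affected subject's change would reverse sign.

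**Conclusion.** The point holds for PROMIS-29/25 at 12 and 24 months, and at 6 months only when Visit 7 is held in months 6 to 7. It holds to a lesser degree for MOxFQ. Contralateral surgery from month 6 is compliant, and no listed item at Visits 7–9 records it.

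The size is unknown. The 0.25–1.0 point illustration rests on assumed shares and losses, and its upper end needs a large share of subjects to have the second operation. On those assumptions the affected values would make the index procedure look less beneficial on PROMIS than it is.

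It would be wrong to conclude that pain by VAS, joint motion or recurrence results are compromised, or that the six-month visit is the main problem. This is an inexpensive improvement to a secondary analysis.

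**What to change.** - **eCRF, Visits 7–9:** add one item asking whether the contralateral foot has been operated on since the last visit (yes/no, date, procedure), and add it to Protocol 7.7–7.9 and the schedule.
- **Protocol 7.7:** state that where contralateral surgery is already planned, the Visit 7 questionnaires are completed before it, within the existing window.
- **MOxFQ:** confirm in Protocol 7.12 and SAP 6.4.4 that it is answered and scored for the index foot.
- **SAP 7.2.2 item 11:** report the number of subjects affected at each visit. Add a sensitivity analysis of PROMIS, and secondarily MOxFQ, that excludes values collected within a pre-specified period after contralateral surgery, for example 4 months. The main analysis is unchanged.

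The time limit matters. Under the even-spread illustration, 420 of 540 days (78%) lie outside the 120 days before a day-720 Visit 9, so excluding every value after surgery would mostly drop subjects already past that period. The VAS does not need this exclusion.

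The cost is one extra question, one extra table and fewer values in the sensitivity analysis. No change to the six-month clinical rule is proposed.
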